3.3 Selection of Subjects

Study entry is open to adults regardless of gender or ethnic background. While there will be every effort to seek out and include women and minorities, the patient population is expected to be no different than that of other advanced metastatic melanoma (cutaneous, unresectable) cancer studies at institutions that have experience in administration of HD IL-2.

4. SUBJECT REGISTRATION

All subjects must be registered through HCRN's electronic data capture (EDC) system. A subject is considered registered when an "On Study" date is entered into the EDC.

Subjects must be registered prior to starting protocol therapy. Subjects must begin therapy **within 7 business days** of registration.

5. TREATMENT PLAN

The primary objective of this single arm phase 2 trial is to assess the response rate [complete response (CR) + partial response (PR)] of sequential therapy of pembrolizumab followed by HD IL-2 in subjects with stage IV malignant melanoma. Response assessment will be performed after pembrolizumab therapy, and response reassessment will be performed after HD IL-2 therapy using revised RECIST 1.1.

5.1 Pembrolizumab Administration

Subjects will receive 200 mg pembrolizumab every 3 weeks for two cycles. Cycle length is 21 days (i.e., 3 weeks). On the last day of Cycle 2 (+ 3 days), disease status will be assessed via imaging. Following the pembrolizumab treatment, HD IL-2 treatment will commence.

Correlative research analyses during pembrolizumab administration include examining the relationship between clinical response at the end of Cycle 2 with PD-L1 expression of the archived diagnostic tumor tissue. Research analyses also include examining the relationship between changes in soluble PD-L1 level and Type 1 T helper cell/Type 2 T helper cell (Th1/Th2) ratios during therapy (assessed after the 2nd dose) relative to baseline and characterization of intestinal microbiome to the best clinical response (RECIST 1.1 criteria) and to treatment outcome.

Drug	Dose	Route	Schedule	Cycle Length
Pembrolizumab	200 mg	Intravenously (IV) over 30 minutes	Day 1 of each cycle	3 weeks (21 days)

¹ A window of - 1 or + 2 days may be applied to all study visits to accommodate observed holidays, inclement weather, scheduling conflicts etc. Date and time of each drug administration should be clearly documented in subject's chart and electronic case report forms (eCRFs).

5.1.1 Pre-Medication for Pembrolizumab Administration

Premedication will be given at the discretion of the site investigator. For patients who experience a Grade 1 or Grade 2 infusion reaction, acetaminophen 650 mg PO and/or 50 mg IV ranitidine (or equivalent H2 antagonist) may be considered prior to subsequent infusions.

5.1.2 Supportive Care for Pembrolizumab

Subjects should receive full supportive care during the study, including transfusion of blood and blood products, treatment with antibiotics, analgesics, erythropoietin, or bisphosphonates, when appropriate.

Although acetaminophen at doses of \leq 2 grams/day is permitted, it should be used with caution in subjects with impaired liver function.

Subjects should receive appropriate supportive care measures as deemed necessary by the treating investigator. Suggested supportive care measures for the management of adverse events that are related to pembrolizumab are outlined below. Where appropriate, these guidelines include the use of oral or intravenous treatment with corticosteroids as well as additional anti-inflammatory agents if symptoms do not improve with administration of corticosteroids. Note that several courses of steroid tapering may be necessary as symptoms may worsen when the steroid dose is decreased. For each disorder, attempts should be made to rule out other causes such as metastatic disease or bacterial or viral infection, which might require additional supportive care. The treatment guidelines are intended to be applied when the investigator determines the events to be related to pembrolizumab.

Pneumonitis

- For **Grade 2 events**, treat with systemic corticosteroids. When symptoms improve to Grade 1 or less, steroid taper should be started and continued over no less than 4 weeks.
- For **Grade 3-4 events**, immediately treat with intravenous steroids. Administer additional anti-inflammatory measures, as needed.
- Add prophylactic antibiotics for opportunistic infections in the case of prolonged steroid administration.
- For guidelines on treatment holds, timing for restarting treatment or discontinuing treatment permanently, see Section 6.1.3, Table 2.

Diarrhea/Colitis

- Subjects should be carefully monitored for signs and symptoms of enterocolitis (such as diarrhea, abdominal pain, blood or mucus in stool, with or without fever) and of bowel perforation (such as peritoneal signs and ileus).
- All subjects who experience diarrhea/colitis should be advised to drink liberal quantities of clear fluids. If sufficient oral fluid intake is not feasible, fluid and electrolytes should be substituted via IV infusion. For Grade 2 or higher diarrhea, consider GI consultation and endoscopy to confirm or rule out colitis.
- For **Grade 2 diarrhea/colitis** that persists greater than 3 days, administer oral corticosteroids.
- For **Grade 3 or 4 diarrhea/colitis** that persists > 1 week, treat with intravenous steroids followed by high dose oral steroids.
- When symptoms improve to Grade 1 or less, steroid taper should be started and continued over no less than 4 weeks.
- For guidelines on treatment holds, timing for restarting treatment or discontinuing treatment permanently, see Section 6.1.3, Table 2.

Type 1 diabetes mellitus (if new onset, including diabetic ketoacidosis [DKA]) or \geq Grade 3 Hyperglycemia, if associated with ketosis (ketonuria) or metabolic acidosis

- For **T1DM or Grade 3-4 Hyperglycemia**
 - Insulin replacement therapy is recommended for Type I diabetes mellitus and for Grade 3-4 hyperglycemia associated with metabolic acidosis or ketonuria.
 - Evaluate patients with serum glucose and a metabolic panel, urine ketones, glycosylated hemoglobin, and C-peptide.

Hypophysitis

- For **Grade 2** events, treat with corticosteroids. When symptoms improve to Grade 1 or less, steroid taper should be started and continued over no less than 4 weeks. Replacement of appropriate hormones may be required as the steroid dose is tapered.
- For **Grade 3-4** events, treat with an initial dose of IV corticosteroids followed by oral corticosteroids. When symptoms improve to Grade 1 or less, steroid taper should be started and continued over no less than 4 weeks. Replacement of appropriate hormones may be required as the steroid dose is tapered.
- For guidelines on treatment holds, timing for restarting treatment or discontinuing treatment permanently, see Section 6.1.3, Table 2.

Hyperthyroidism or Hypothyroidism

Thyroid disorders can occur at any time during treatment. Monitor patients for changes in thyroid function (at the start of treatment, periodically during treatment, and as indicated based on clinical evaluation) and for clinical signs and symptoms of thyroid disorders.

- **Grade 2** hyperthyroidism events (and **Grade 2-4** hypothyroidism):
 - In hyperthyroidism, non-selective beta-blockers (e.g. propranolol) are suggested as initial therapy.
 - In hypothyroidism, thyroid hormone replacement therapy, with levothyroxine or liothyroinine, is indicated per standard of care.
- **Grade 3-4** hyperthyroidism
 - Treat with an initial dose of IV corticosteroid followed by oral corticosteroids. When symptoms improve to Grade 1 or less, steroid taper should be started and continued over no less than 4 weeks. Replacement of appropriate hormones may be required as the steroid dose is tapered.
 - For guidelines on treatment holds, timing for restarting treatment or discontinuing treatment permanently, see Section 6.1.3, Table 2.

Hepatic

- For **Grade 2** events, monitor liver function tests more frequently until returned to baseline values (consider weekly).
 - Treat with IV or oral corticosteroids
- For **Grade 3-4** events, treat with intravenous corticosteroids for 24 to 48 hours.
 - When symptoms improve to Grade 1 or less, a steroid taper should be started and continued over no less than 4 weeks.
 - For guidelines on treatment holds, timing for restarting treatment or discontinuing treatment permanently, see Section 6.1.3, Table 2.

Renal Failure or Nephritis

- For **Grade 2** events, treat with corticosteroids.
- For **Grade 3-4** events, treat with systemic corticosteroids.
 - When symptoms improve to Grade 1 or less, steroid taper should be started and continued over no less than 4 weeks.
 - For guidelines on treatment holds, timing for restarting treatment or discontinuing treatment permanently, see Section 6.1.3, Table 2.

Management of Infusion Reactions

- Signs and symptoms usually develop during or shortly after drug infusion and generally resolve completely within 24 hours of completion of infusion.
- See Table 1 in Section 6.1.2, Management of Allergic Reaction/Hypersensitivity, for detailed information on how Grades 1-4 reactions are treated.

5.2 HD IL-2 Administration

After completing the 2 cycles of pembrolizumab, High Dose Interleukin-2 (HD IL-2) will be administered. This will require a hospital stay of at least 5 days for each treatment cycle. Established guidelines will be followed for safely administering HD-IL-2 and managing toxicities from this treatment [31,32]. Two treatment cycles will be administered, Cycle 2 being separated from Cycle 1 by approximately 9 days after completion (assuming subject has recovered from Cycle 1 adequately to proceed with Cycle 2). Four weeks after completion of the 2 cycles (called a course of HD IL-2 therapy), disease status will be monitored via CT of the chest and abdomen/pelvis using revised RECIST guidelines (version v1.1, Section 9 of protocol).

Correlative research analyses in this phase include examining the relationship between changes in soluble PD-L1 level and Type 1 T helper cell/Type 2 T helper cell (Th1/Th2) ratios assessed after each of the two HD IL-2 cycles relative to baseline (i.e., pre-dose on Day 1 of Cycle 1 of pembrolizumab treatment), to the best clinical response (modified RECIST criteria) and to treatment outcome.

Drug	Dose	Route	Schedule	Cycle Length
IL-2	600,000 IU/kg ²	Intravenously (IV) over 15 minutes	Every 8 hours for up to 14 doses over 5 days	Days 1-5 = Cycle 1 9 days of rest in between Days 15-19 = Cycle 2

¹ A window of - 1 or + 2 days may be applied to all study visits to accommodate observed holidays, inclement weather, scheduling conflicts etc. Date and time of each drug administration should be clearly documented in subject's chart and electronic case report forms (eCRFs).

²Actual weight will be used unless the patient is 30% over ideal body weight in which case adjusted body weight will be used (Males: IBW = 50 kg + 2.3 kg for each inch over 5 feet.

Females: IBW = 45.5 kg + 2.3 kg for each inch over 5 feet); ABW = IBW + 0.4(actual weight - IBW)

5.2.1 Supportive Care specific to HD IL-2

Subjects should receive appropriate supportive care measures as deemed necessary by the site investigator. Several treatment-related toxicities have been uniquely associated with the administration of HD IL-2. Suggested management are listed in the Study Procedures Manual (SPM).

5.3 Concomitant Medications

Medications or vaccinations specifically prohibited in the exclusion criteria are not allowed during the ongoing trial. If there is a clinical indication for one of these or other medications or vaccinations specifically prohibited during the trial, discontinuation from trial therapy or vaccination may be required. The final decision on any supportive therapy or vaccination rests with the site investigator and/or the subject's primary physician.

5.3.1 Allowed Concomitant Medications

All treatments that the investigator considers necessary for a subject's welfare may be administered at the discretion of the investigator in keeping with the community standards of medical care. All concomitant medications will be recorded on the electronic case report form (eCRF).

All concomitant medications received within 28 days before the first dose of trial treatment and 30 days after the last dose of trial treatment should be recorded. Concomitant medications administered beyond 30 days after the last dose of trial treatment should be recorded for SAEs and ECIs.

Myeloid growth factors to treat subjects with neutropenia according to the American Society of Clinical Oncology (ASCO) Guidelines are permitted. Myeloid growth factors should be avoided (if medically appropriate) in Cycle 1 until subjects have developed a dose-limiting Grade 4 neutropenia.

Antiemetic agents may be administered at the discretion of the site investigator but are not commonly required as a prophylactic agent. All other manifestations of the subject's malignancy should be treated at the discretion of the investigator.

Medications with potential central nervous system (CNS) effects are not prohibited in this study, but it is recommended that their use be minimized to avoid confusion in the interpretation of CNS effects should they occur during the course of treatment with pembrolizumab.

In appropriate settings, such as combinations with agents known to produce frequent thrombocytopenia, restricted uses of anticoagulants should be considered.

All other medical conditions should be treated at the discretion of the site investigator in accordance with local community standards of medical care.

5.3.2 Prohibited Concomitant Medications

Subjects are prohibited from receiving the following therapies during the Screening and Pembrolizumab Treatment Phase of this trial:

- Anti-cancer systemic chemotherapy or biological therapy not specified in this protocol
- Immunotherapy not specified in this protocol
- Concomitant use of chemotherapy
- Investigational agents
- Radiation therapy
- Note: Radiation therapy to a symptomatic solitary lesion or to the brain may be allowed after consultation with study chair.
- Live vaccines within 30 days prior to the first dose of trial treatment and while participating in the trial. Examples of live vaccines include, but are not limited to, the following: measles, mumps, rubella, chicken pox, yellow fever, rabies, BCG, and typhoid (oral) vaccine. Seasonal influenza vaccines for injection are generally killed virus vaccines and are allowed; however, intranasal influenza vaccines (e.g. Flu-Mist[®]) are live attenuated vaccines, and are not allowed.

- Systemic glucocorticoids for any purpose other than to modulate symptoms from an event of clinical interest of suspected immunologic etiology. The use of physiologic doses of corticosteroids may be approved after consultation with the sponsor-investigator.

Subjects who, in the assessment by the site investigator, require the use of any of the aforementioned treatments for clinical management should be removed from the trial.

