5.5 Use in Pregnancy

If a subject inadvertently becomes pregnant while on study treatment, the subject will immediately be removed from the study. The site will contact the subject at least monthly and document the subject's status until the pregnancy has been completed or terminated. The outcome of the pregnancy will be reported to Hoosier Cancer Research Network (HCRN) **within 1 business day** if the outcome is a serious adverse experience (e.g., death, abortion, congenital anomaly, or other disabling or life-threatening complication to the mother or newborn). HCRN will report this information **within 1 business day** to Prometheus. The study investigator will make every effort to obtain permission to follow the outcome of the pregnancy and report the

condition of the fetus or newborn to HCRN. If a male subject impregnates his female partner, he must immediately inform the site study personnel and the pregnancy reported and followed as described above.

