6.1 Dose Delays for Pembrolizumab Administration

6.1.1 Start of a New Cycle

A new treatment cycle will only be initiated when all of the following conditions are met:

- ANC $\geq 1,500 \times 10^9/L$
- platelets $\geq 100 \times 10^9/L$
- Non-hematologic treatment related toxicities have improved to \leq Grade 1 or to the subject's baseline values (except alopecia)

If blood counts (first two bullet points above) are below this threshold, blood work is to be repeated weekly until counts are at an acceptable level. If treatment is unable to restart within 12 weeks of the planned treatment date, the subject will be permanently discontinued from study therapy.

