6.1.2 Management of Hypersensitivity Reaction

Table 1: Management of allergic reaction/hypersensitivity based on CTCAE Grade

Description	Action
Grade I Allergic Reaction/Hypersensitivity: (Transient flushing or rash, drug fever < 38°C):	Supervise without further treatment for allergic reaction/hypersensitivity.
Grade 2 Hypersensitivity Reaction: (Rash, flushing, dyspnea, urticaria, drug fever greater than or equal to 38°C) and/or asymptomatic bronchospasm:	Interrupt the infusion. If symptoms abate, attempt re-infusion at a slower rate. If the symptoms recur, discontinue infusion and follow for recurrent allergic reaction/hypersensitivity in the next paragraph.
Recurrent Grade 2 or Grade 3 or 4 Hypersensitivity Reaction:	Stop the infusion. Administer additional doses of H1 and H2 blockers intravenously. Administer IV steroids and consider epinephrine and bronchodilators as clinically indicated.
Grade 3 or 4 Hypersensitivity Reaction:	Will be permanently discontinued from study treatment.

Prior to re-challenge of Grade 2 allergic reaction/HSR and if there is a subsequent cycle, the following prophylactic premedications are recommended prior to the pembrolizumab infusion: give both an H1 and H2 blocker intravenously within 30 to 60 minutes before pembrolizumab infusion. If treatment delay necessitates a period longer than 12 weeks, treatment is stopped and the subject is discontinued from the study.

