6.2 Protocol Therapy Discontinuation

In addition to discontinuation from therapy related to toxicities as outlined above, a subject will also be discontinued from protocol therapy and followed per protocol under the following circumstances outlined below. The reason for discontinuation of protocol therapy will be documented on the electronic case report form (eCRF)

- Documented disease progression
- Site investigator determines a change of therapy would be in the best interest of the subject
- Subject requests to discontinue protocol therapy, whether due to unacceptable toxicity or for other reasons
 - In a subject decides to prematurely discontinue protocol therapy (“refuses treatment”), the subject should be asked if he or she may still be contacted for further scheduled study assessments. The outcome of that discussion should be documented in both the medical records and in the eCRF.
- Female subject becomes pregnant
- HD IL-2 will be discontinued if there is a ≥ 12 -week delay between cycles
- Pembrolizumab will be discontinued if there is a ≥ 12 -week delay between cycles

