- 11: The safety follow-up visit should occur when subjects permanently stop study treatment for whatever reasons (toxicity, progression, or at discretion of site investigator) and should be performed 30 days (± 7 days) after the last dose of treatment. Subjects who have an ongoing Grade \geq 2 or serious AE (SAE) at this visit will continue to be followed until the AE resolves to \leq Grade 1 or baseline, deemed clinically insignificant, and/or until a new anti-cancer treatment starts, whichever is earlier.
- 12: Long-term follow up will occur in all subjects after the safety follow up visit. Subjects who discontinue treatment for any reason will be followed every 3 months for 12 months. Follow up may be accomplished via clinic visit, phone call, or other avenues as appropriate.

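### Sections 5.3.2, 5.5 and 6.1.2 take subjects off the trial for events that other sections treat as stopping therapy only, so follow-up, chiefly for PFS, may end under one reading

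*Combined protocol and SAP*

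**What the plan says.** Three events lead to different states depending on the section read.

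| Event | Removal wording | Therapy-only wording |
|---|---|---|
| Need for a prohibited therapy | 5.3.2: subjects who "require the use of any of the aforementioned treatments for clinical management should be removed from the trial" | 5.3 (parent section): "discontinuation from trial therapy or vaccination may be required" |
| Pregnancy | 5.5: "the subject will immediately be removed from the study" | 6.2 Protocol Therapy Discontinuation lists it among the cases where "a subject will also be discontinued from protocol therapy and followed per protocol" |
| Delay of about 12 weeks | 6.1.2: "treatment is stopped and the subject is discontinued from the study" | 6.1.1: "the subject will be permanently discontinued from study therapy"; 6.2 also lists a 12-week delay as a reason to stop the drug |

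The 5.3.2 list has a limited scope: "Subjects are prohibited from receiving the following therapies during the Screening and Pembrolizumab Treatment Phase of this trial".

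Calendar footnote 12 applies to everyone: "Subjects who discontinue treatment for any reason will be followed every 3 months for 12 months". Footnote 11 gives a safety visit whatever the reason for stopping. Section 6.3 treats leaving the protocol as distinct from leaving protocol therapy. Section 12.1 describes progressing subjects as off the study and, in the same sentence, as still followed for survival.

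**The concern.** Because 6.3 recognises two states, the choice of words has consequences. A site that takes 5.3.2, 5.5 or 6.1.2 literally may stop scanning and following the subject. A site that applies 6.2 and footnote 12 would not. The data would then depend on which section was read.

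Two analyses are exposed.

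- **PFS.** The objective covers all enrolled subjects, and 9.9.7 censors those without progression at their last disease evaluation. Needing radiation or another anticancer drug plausibly signals worsening disease. Censoring for that reason would be informative, and Kaplan-Meier does not correct for it.
- **Response rate.** The 5.3.2 rule acts during the pembrolizumab phase, and the first post-baseline scan comes at the end of that phase (Cycle 2 Day 21). Under 12.4 a subject is evaluable after at least one dose plus either a post-baseline assessment or death before any evaluation, and unevaluable subjects are replaced. Someone removed before that scan may drop out of the denominator.

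**Working it through.** The contradiction is textual and needs no arithmetic. The calculations below only indicate what it could cost. All removal fractions and hazard ratios are assumptions, because the documents give none.

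**1. The plan's design figures (12.3).** Inputs: p0 = 0.26, p1 = 0.50; stop if 3 or fewer of 11 respond; reject the drug if 11 or fewer of 29 respond.
- Early stopping under p0: sum over x = 0 to 3 of C(11,x) × 0.26^x × 0.74^(11−x) = 0.685, as stated. Probability of stage 2: 1 − 0.685 = 0.315, as stated.
- Exact two-stage type I error 0.043; power 0.807. The design reproduces.

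**2. PFS if removed subjects are censored.** Assume exponential times, a fraction f censored at 1.5 months (near the end of two 21-day cycles), and hazard ratio h in that fraction afterwards. As reference for retained subjects, use the 6-month PFS of 46.4% that section 1.2 gives for pembrolizumab every 3 weeks.
- λ = −ln(0.464)/6 = 0.128 per month.
- Kaplan-Meier with censoring returns 0.464.
- True rate = (1 − f) × 0.464 + f × exp(−1.5λ) × exp(−4.5hλ).
- Example, f = 0.10 and h = 2: 0.9 × 0.464 + 0.1 × 0.825 × 0.316 = 0.444, a bias of 2.0 points.

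| f | h = 1 | h = 2 | h = 3 |
|---|---|---|---|
| 5% | 0.0 | 1.0 | 1.6 |
| 10% | 0.0 | 2.0 | 3.2 |
| 20% | 0.0 | 4.1 | 6.3 |

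(Upward bias in 6-month PFS, percentage points.)

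**3. OS, only if reported in all subjects.** The same formula with the 12-month survival of 68.4% from section 1.2 gives 1.0 points (f = 5%, h = 2) to 6.6 points (f = 20%, h = 3), and 0 at h = 1.

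**4. Model-free bound.** With 29 subjects, each one of unknown status leaves 1/29 = 3.4 points undetermined in a 12-month rate; three leave 3/29 = 10.3 points.

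**5. Response rate if removed subjects are replaced.** Assume a true rate of 0.26 in all treated subjects, and that a fraction f, all non-responders, is removed before any assessment and replaced. The rate among evaluable subjects is then 0.26/(1 − f). Applying the plan's decision rule:

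| f | Evaluable rate | Chance of declaring the regimen active |
|---|---|---|
| 0 | 0.260 | 0.043 |
| 5% | 0.274 | 0.061 |
| 10% | 0.289 | 0.087 |
| 20% | 0.325 | 0.173 |

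This is the unfavourable case: every removal must precede the first assessment and be classed as unevaluable.

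**The case against.** The best defence is that the plan already keeps these subjects. Footnote 12 follows everyone, footnote 11 provides the safety visit, and 12.1 shows that off study need not mean off follow-up. Section 6.3 concerns a subject's own decision to withdraw and even then asks that assessments be completed as far as possible. Section 5.5 requires at least monthly contact during the pregnancy. This stands to the extent that loss of data is a risk under one reading and not something the plan prescribes. It does not remove the conflict: 12.1 says that survival follow-up continues, 5.3.2 and 6.1.2 say nothing of the kind, and the contact in 5.5 concerns the pregnancy. It also does not protect PFS, because the calendar's long-term column lists only survival status and subsequent therapy, with no scans.

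Several stronger readings are tempting but unsupported.

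- **A large bias in the OS objective.** If true 12-month OS were 60% in 29 subjects and six with 20% survival dropped out early, reported OS would be (29 × 0.60 − 6 × 0.20)/23 = 70.4%. But the OS objective covers only subjects with response or stable disease after two cycles of each drug. Subjects removed during pembrolizumab would generally fall outside it. The calculation bears only on the unrestricted OS wording in 2.2.2, and neither the six nor the 20% comes from the documents.
- **Loss of late safety data.** AE recording ends 30 days after HD IL-2 for everyone (11.2.1). What could be lost is the safety visit and follow-up of unresolved events.
- **A poor-prognosis group throughout.** This is plausible for radiation or other anticancer therapy. The documents show no such link for pregnancy, live vaccines or a delay after hypersensitivity. Subjects with documented progression are already PFS events.
- **Protocol management that itself triggers removal.** One could argue this from the radiation note in 5.3.2 and the IV steroids in Table 1 of 6.1.2. The note can be read as an exception to the ban, and the steroid argument depends on whether a reaction counts as immunologic. Both need clarifying, but neither is a demonstrated contradiction.

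**Conclusion.** The point holds as an inconsistency with a possible analytic cost. For all three events, the removal wording and the therapy-only wording cannot both be followed if removal means leaving follow-up. PFS is the main exposure, and the response rate is exposed through the replacement rule in 12.4. OS is affected only if reported in all subjects, and the safety exposure is small.

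The size is unknown. Under the assumed 5 to 20% removal and hazard ratios of 2 to 3, 6-month PFS is overstated by 1.0 to 6.3 points. Type I error could rise from 0.043 to between 0.061 and 0.173 if all removals were unassessed non-responders who were replaced. If removal is unrelated to prognosis, the PFS bias is zero; if follow-up is kept, neither the PFS nor the OS bias arises. The change is worth making because it is cheap and the trial has at most 29 subjects.

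**What to change.** 1. Reconcile 5.3.2, 5.5 and 6.1.2 with 5.3, 6.1.1 and 6.2, so that none of these events by itself ends study follow-up.
2. State that these subjects remain followed per protocol: the 3-monthly scans of 12.1 until progression or one year for those without progression, plus survival follow-up. Show the scans in the calendar's long-term column, since footnote 12 alone does not secure PFS.
3. Reserve off-study status for withdrawal of consent, loss to follow-up, death or end of follow-up.
4. Count these subjects in the response denominator and do not replace them.
5. Record the date and type of any prohibited therapy.

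Whether and when treatment stops is for the sponsor to reconcile, including the discretionary wording of 5.3 against the closing sentence of 5.3.2, and how that sentence fits its radiation note and the steroid use in Table 1. No clinical rule is proposed here.

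The cost is wording changes and a few additional scans and follow-up contacts. The sample size and decision rule do not change.
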